## 1 List of Abbreviations

Abbreviation	Abbreviation definition
ADHD	Attention Deficit/Hyperactivity Disorder
BU	Boston University
BMC	Boston Medical Center
CHW	Community Health Worker
WECARE	W ell Child Care, E valuation, C ommunity, Resources, Advocacy, Referral, Education
PRE-CARE	P REschooler care, C ommunity resources, Advocacy, Referral, Education

## 2 Protocol Summary

Title:	Pilot testing PRE-CARE to address unmet social needs for preschoolers with inattention and/or hyperactivity
Population:	60 English and Spanish-speaking primary caregivers of preschool aged children with symptoms of inattention and/or hyperactivity, with or without a previous clinical diagnosis of ADHD
Intervention:	"PRE-CARE": Bachelors-level interventionist-delivered low intensity, family-centered screening, referral, and patient navigation program adapted from the WE CARE program
Objectives:	To develop an early intervention strategy targeting unmet social needs for low-income families of preschool-age children with emerging ADHD.
Design/Methodology:	An adaptive randomized, controlled pilot study.
Total Study Duration:	Approximately 1 year
Subject Participation Duration:	12 months (assessment timepoints at baseline, 3 months, 6 months, and 12 months)

## 3 Background/Rationale & Purpose

### 3.1 Background Information

Attention-Deficit/Hyperactivity Disorder (ADHD) is one of the most common chronic conditions in childhood, most often beginning in the preschool years. While ADHD is in part heritable, social and environmental determinants contribute significantly to its development and expression. Socioeconomic disadvantage and associated social adversities emerge as strong risk factors for ADHD as early as the preschool years. These stressors predict more severe illness, poor functioning, inferior response to treatments, and worse outcomes. Therefore, addressing unmet social needs - such as food insecurity, housing instability, and lack

of quality child care - could be a powerful early intervention for preschool-age children with ADHD symptoms, altering the life course of this chronic condition.

However, there is a critical gap in understanding how unmet social needs influence ADHD illness trajectory; the degree to which individual needs impact ADHD risk; and whether addressing remediable unmet social needs in young children with ADHD symptoms could reduce the socioeconomic disparity in ADHD outcomes. Adapting an intervention to target preschoolers with emerging ADHD, who are typically first identified in primary care, could significantly impact symptoms and functioning, as well as improve clinical outcomes in this crucial developmental stage. This highlights the need for intervention methods in preschool aged children that account for social, economic, and environmental stressors, including low income, low parental education level, housing instability, food insecurity, single parenthood, prenatal smoking and illicit drug use, community violence, parental incarceration, and familial mental illness. Using the framework for the NIH stage model for behavioral interventions, we have developed an intervention to identify and alleviate unmet social needs in families of young children with emerging ADHD symptoms.

[name], pediatrician and pioneer in the field of addressing unmet social needs as part of medical care, has shown that a low intensity, family-centered screening and referral program (WE CARE) at well infant visits is feasible and can increase receipt of resources for unmet social needs (e.g. food, transportation, and parent education). Others have shown that a similar intervention paired with navigation to services (i.e. assistance from staff to find and access resources) could improve general child health. The American Academy of Pediatrics now recommends social needs screening and referral to community resources at well child visits. Adapting this strategy to target preschoolers with emerging ADHD, who are typically first identified in primary care, could significantly impact clinical symptoms and disease trajectory during a critical developmental period, and yet a time when there are few known effective treatments. Therefore, our overarching goal is to develop and pilot test a novel early intervention strategy targeting remediable unmet needs for families of low-income, preschool-age children with inattention and/or hyperactivity symptoms, which could be a sign of emerging ADHD.

We conducted in-depth interviews with parents of preschool aged children with emerging ADHD symptoms to gain a deeper understanding of how unmet social needs affect symptoms and functioning in young children with ADHD and intervention preferences. Using this rich data from families and guided by experts, we have developed an intervention by adapting the WE CARE screening and referral model originally developed for well infant visits. We have adapted WE CARE in several key domains: for a new target population (preschoolers with emerging ADHD), incorporating new content (e.g., needs particular to this age group and disease, such as special education and parent mental health care), and primary outcome (ADHD symptoms). Our new intervention is called PRE-CARE (PREschooler care, Community resources, Advocacy, Referral, Education), and includes three core components: (1) screening for unmet needs, (2) providing families with written resource sheets listing community-based referrals tailored to their needs, and (3) providing families with family navigation support to assist them with connecting to community resources. This study will be conducted in compliance with the

protocol, applicable regulatory requirements, and BMC/BU Medical Campus Human Research Protection policies and procedures.

### 3.2 Rationale and Purpose

The goal of this proposed study is to pilot test a novel treatment model (PRE-CARE) addressing unmet social needs for families of preschool-age children with ADHD symptoms. We will conduct an adaptive, pilot randomized controlled trial (RCT) of the intervention with parents of 60 low-income children age 3-5 (36-71 months) with ADHD symptoms in order to: optimize intervention delivery; field test study logistics (e.g., recruitment, enrollment, randomization, retention); explore putative intervention mechanisms; and obtain estimates of study parameters to plan an appropriately powered RCT of the intervention. The PRE-CARE intervention is adapted from WE CARE, a screening and referral intervention that has been shown to be feasible and effective in addressing the family psychosocial stressors of low-income families seen in pediatric medical homes. Given the negative impact that socioeconomic stressors can have on the health and development of young children with ADHD symptoms, tailored interventions such as PRE-CARE may serve as a vital early intervention strategy to promote long-term well-being.

## 4 Objectives

### 4.1 Study Objectives

Our aim is to enroll 60 subjects (30 intervention, 30 control). Because this is a pilot study, it is not fully powered to detect differences between groups. Our main objectives are as follows:

- Field test study logistics: We will record the number of families approached, screened, ineligible, refusing participation, and enrolled; rate of recruitment and referring provider/site; intervention attrition and study retention; adverse events; and collect participant feedback via detailed exit interviews.
- Optimize intervention delivery: We will collect process measures for intervention optimization including the number of contacts and length of time per contact, referrals made and resources received, time to resolution of each unmet need, and participant feedback.
- Explore putative intervention mechanisms: We will do this via participant exit interviews and parent-report questionnaires. We will power a future study for detection of target engagement using the parameters obtained. Our proposed measures of target engagement are unmet social needs (decrease expected); parent stress (decrease expected); parent activation (increase expected), and child/parent mental health service use (increase expected). These may change based on formative work and participant feedback.

### 4.2 Study Outcome Measures

#### 4.2.1 Primary Outcome Measures

**Primary outcomes** include the following clinical outcomes:

- ADHD Symptoms (ADHD-RS-IV Preschool Version)
- Child Psychiatric Symptoms (Child Behavior Checklist 1.5-5)

**Secondary outcomes** include the following measures of unmet social needs, treatment access and utilization, parent activation, parent mental health/stress, adverse childhood experiences, and feasibility/acceptability:

- Unmet Social Needs Outcomes (Children's Health Watch Vital Signs and National Survey of Children's Health pertaining to all unmet needs in the PRECARE Screener).
- Adverse Childhood Experiences (CYW ACE-Q)
- Parental Depression (PHQ-9)
- Parental ADHD (ASRS-v1.1)
- Global Perceived Stress (PSS)
- Parenting Stress (PSI-SF)
- PRE-CARE Feasibility and Acceptability Questionnaire
- Semi-structured in-depth exit interviews with parent/guardians on feasibility/acceptability

**Process outcomes** include the following measures of study and intervention processes:

- **Recruitment and enrollment statistics** (number of parent/guardians referred and from which clinic, contacted, screened, eligible, refused participation, enrolled, dropped out of study or intervention early and why, and completed intervention)
- **Contacts with parent/guardians** (number, frequency, modality, length)
- **Referrals made** (including agencies, date of referral, and parent/guardian vs. staff referral)
- **Resources accessed** (including specific resource accessed, resource category, date accessed)
- **Needs resolved** (date at which a participant indicates they no longer need help with a need and why)

## 5 Study Design

This study is a pilot randomized control trial. Participants are parents of preschool aged children between the ages of 3-5 years old with either an ADHD diagnosis OR with a score  $\geq$  80th percentile on the Preschool Version of the ADHD Rating Scale-IV. Potentially eligible participants will be referred to the study team by pediatric providers via the electronic medical record (EMR), or identified via EMR screening. Following eligibility screening, informed consent, and completion of baseline questionnaires, participants will be randomly assigned to treatment methods of either the interventional treatment (PRE-CARE) or control treatment (care as usual). All participants will be sent baseline and follow-up questionnaires to complete either electronically via REDCap, in-person with an RA using pencil/paper, or verbally with an RA (depending on participant preference). Participants randomized to PRE-CARE will also complete feasibility and acceptability measures including an exit interview.

Participants assigned to the PRE-CARE arm will be asked to complete the PRE-CARE self-report screener including 16 questions that assess 14 social needs categories (childcare, employment, housing, food, parent education, utilities, public benefits, tax filing, child education, child healthcare, child behavioral/mental health services, child after school activities, parent healthcare, and parent mental health services). Following completion of the screener, they will meet with a BA-level interventionist (either in person or virtually via videoconference) in which the interventionist will review the screening responses with the participant and assess in more detail what help is needed and possible. The interventionist will provide the participant with a Family Resource Booklet (physically and/or electronically) containing written resources corresponding to the 14 categories reflected on the PRE-CARE screener. The interventionist will provide the participant with any additional care coordination and referral support needed to ensure that the family is able to access needed community resources. Meetings will be scheduled bi-weekly, with additional contact as needed, until three months have passed. If the needs and issues require longer than three months to resolve, participants may continue their intervention period even after three months have passed in order to complete all the ongoing support. Participants may also end their intervention period before three months have passed if they no longer need support and all needs have been resolved. Interventionists will provide PRE-CARE participants with their contact information and serve as an available resource to support families throughout the duration of the intervention period.

Participants assigned to the control condition will receive care as usual within their pediatric primary care practice. At many Boston Medical Center-affiliated pediatric practices, this involves social needs screening at medical visits with provision of resources and referral to integrated behavioral health providers for assistance with short term treatment and referrals to other behavioral health services as needed. There will be no research staff-initiated contact with control subjects between baseline and follow up questionnaires. If control subjects contact research staff we will follow standard clinical or BMC procedures depending on the nature of the contact or concern. If they call to ask about a resource (e.g., obtaining food), we will provide information about BMC services or community organizations that could help with that resource. For most concerns both clinical and social, we will direct them to their primary care provider's office for additional support. If there is a safety concern we will follow our safety protocol, as in the intervention group as well.

Participants in the intervention arm will communicate with primary care providers about referrals completed, and enter this information into the medical record. Furthermore, participants may already have been referred to resources prior to enrollment in the study. In that case, interventionists will communicate with usual care providers and staff to be sure they are aware of the family's participation, and coordinate accordingly on the provision of needs. Families in the intervention arm or in the control arm will NOT be restricted on what they can access in the clinical setting.

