***Intervention Part 3, Resource Navigation.*** Interventionists will discuss further with families the details of specific needs indicated during screening in order to best tailor assistance provided. Based on this conversation, the interventionist may offer more intensive support navigating to certain resources for families where it is needed. Interventionists will have a companion Navigation Resource Booklet that includes workflows and algorithms to assist with referral decisions for families. The level of interventionist involvement will be based on the family's particular needs, community resources available, and a shared decision-making process between the interventionist and family. For example, some participating parents may choose to

simply contact agencies listed in the Family Resource Booklet on their own, and not request any further support from the interventionist. Other families may want more assistance contacting and accessing community resources. In these cases, the interventionist may place referrals, coordinate services, or contact community agencies and providers on behalf of the family to inquire about resources.

As a default, the interventionist will offer follow-up meetings with the participating caregiver (either in-person, by phone, or via videoconference) every two weeks until three months have passed since the randomization date. The interventionist may end the intervention period later for the participant whose needs require longer than three months to resolve. The interventionist may also end the intervention period earlier than three months for the participant if all needs mentioned by the participant have been resolved. All forms of interventionist contacts (in-person appointments, emails, phone, and text message exchanges) and community resources placed on behalf of participating families will be documented in the participant's electronic medical record and logged by the interventionist in the study record. Interventionists will also log the length of time per contact. At each contact, interventionists will also inquire about resources received since last contact, and about whether additional help is needed for that need, or other (even new) needs. They will also ask for feedback about resources received and our process for helping families. Contacts will vary in time length (e.g., 5-10 minute calls vs. 1 hour long meetings) depending on the needs of each family.

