### **Randomization Procedures**

Once a caregiver gives consent to enroll in the study, they will be provided with a unique ID number and this ID number will be connected to their identifiable data (access to identifiable data will be limited to only research staff members and investigators listed on the IRB). Once consent and baseline assessment are completed, the caregiver/family will be randomized. Participants will be randomized to either the PRE-CARE intervention or to the care as usual control condition through the computerized randomization feature of REDCap. If a participating caregiver has multiple eligible children, they will be randomized by family. Randomization will be stratified by primary language (English and Spanish). Due to the nature of the intervention, we will not be able to blind study participants or research assistants serving as interventionists. Study assessments will be completed by parents independently, but if assistance is needed, it will be provided by a separate research staff member who is not the interventionist.

After the random assignment has been generated in REDCap, research staff will contact participants by phone to share their assignment, and with their permission, also inform the clinical care team of the study assignment. If a participant is randomized to the PRE-CARE intervention, research staff will then schedule their first study visit with the family. Research staff will aim to schedule this first study visit as soon as possible, preferably within one week of the date that the random assignment was generated. If a participant is randomized to care as usual, the parent will be advised to follow up with their clinical providers to determine the next steps for their child's treatment according to the standard of care at their clinical site. Clinical providers will also be advised that the family has been randomized to care as usual. Results of psychometric tools (i.e., CBCL 1.5-5 and ADHD-RS-IV-Preschool Version) will be shared with providers for all families with permission of the participating parent. Research staff will not contact the families in the control condition again until the time of follow-up assessments at 3, 6, and 12 months following completion of baseline assessments.

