Participants may be removed if:

1. If the study investigator or treating provider feels the study is negatively impacting the participant’s health or wellbeing resulting in increasing severity of illness that is clinically assessed as such by the study PI. The interventionist and study PI will have weekly meetings/supervision to evaluate study progress, and discuss and address any concerns about participant risk. Any cases of a parent reporting that either their child’s ADHD symptoms or their own parental mental health symptoms are worsening will be assessed clinically and study PI will determine whether the participant should be removed from the study and whether an adverse event or unanticipated problem should be filed.
2. If the participant presents with clinically determined safety risk to self or others.

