## 10 Assessment of Safety and Data Safety Monitoring Plan (DSMP)

### 10.1 Definitions

The following definitions will be used in the assessment of safety:

*Adverse Event (AE)* is defined as an event or group of events together that pose potential physical, emotional, legal or financial risk that is/are plausibly related to the research intervention and/or research procedures. Thus, AEs in this study could include any substantial or significant changes to the participant's mental health and symptoms, abnormal or harmful behaviors, suicidal behavior or attempts, or breach in the protection of participant data or breach of confidentiality because they are plausible in regards to our study intervention/procedures. We will document such AEs, whether or not considered related to the participants' participation in the research. The investigator or designee will make a determination regarding relatedness to the study intervention and/or procedures. We will not track physical signs and symptoms, abnormal lab results, new diagnoses, etc. as AEs.

*Serious Adverse Event (SAE)* is any adverse event that

- (1) results in death;
- (2) is life-threatening;
- (3) results in inpatient hospitalization or prolongation of existing hospitalization;
- (4) results in a persistent or significant disability/incapacity;
- (5) results in a congenital anomaly/birth defect; or
- (6) based upon appropriate medical judgment, may jeopardize the subject's health and well-being and requires hospitalization, other mental health or medical stabilization, child protection services or other higher level of care

*Life-threatening* means that the event places the subject at immediate risk of death from the event as it occurred.

*Unanticipated Problem* is defined as an event, experience or outcome that meets **all three** of the following criteria:

- is unexpected; AND
- is related or possibly related to participation in the research; AND
- suggests that the research places subjects or others at a greater risk of harm (including physical, psychological, economic, or social harm) than was previously known or recognized.

*Possibly related* means there is a reasonable possibility that the incident, experience, or outcome may have been caused by the procedures involved in the research

*Unexpected* means the nature, severity, or frequency of the event is not consistent with either:

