**Data Safety Monitoring Board**

In addition, because this project includes an intervention intended to impact clinical outcomes, the inclusion of a Data and Safety Monitoring Plan and Board is appropriate. The Data and Safety Monitoring Board (DSMB) will include an independent group of experts on child behavioral health, clinical trials, and biostatistics, who will advise and monitor the project with the study principal investigator (PI). None of the members will directly supervise, report to, or directly collaborate with the PI. The following three members will serve on the DSMB:

- 1) **[name] [name]**, Assistant Professor in Department of Child and Adolescent Psychiatry, Johns Hopkins University/Johns Hopkins Bayview Medical Center
- 2) **[name]**, Vice Chair for Research in Pediatrics, University of Massachusetts Medical School
- 3) **[name] [name]**, Research Associate Professor of Health Law, Policy, and Management at the Boston University School of Public Health

The DSMB will meet every six months (+/- 30 days for flexible scheduling). Its primary responsibilities will be to:

- 1) Review and evaluate the accumulated study data for participant safety, study conduct and progress, and efficacy; and
- 2) Make recommendations concerning the continuation, modification, or termination of the trial.

In this proposed project, the DSMB will consider study-specific data and any concerns for poor clinical outcomes among patients in a particular randomization condition. As part of their responsibility, DSMB members will ensure the timeliness, completeness, and accuracy of the data submitted to them for review. Members will ensure submitted data are sufficient for evaluation of the safety and welfare of study participants. The DSMB will also assess the performance of overall study operations and any other relevant issues, as necessary.

Specific items to be reviewed by the DSMB will include:

- Interim/cumulative data for evidence of study-related adverse events;
- Interim/cumulative data for evidence of efficacy according to pre-established statistical guidelines;
- Data quality, completeness, and timeliness;
- Adequacy of compliance with goals for recruitment and retention, including those related to the participation of women and minorities;
- Adherence to the protocol;
- Factors that might affect the study outcome or compromise the confidentiality of the trial data; and

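### Adverse events are looked for more often in PRE-CARE than in controls, with no inquiry common to both arms, so recorded counts would probably run higher in PRE-CARE early on even at equal true risk

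*Combined protocol and SAP*

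**What the plan says.** **Contact in PRE-CARE.** Section 5 states: "Meetings will be scheduled bi-weekly, with additional contact as needed, until three months have passed". Section 8 (Resource Navigation) repeats the default, with meetings offered "every two weeks until three months have passed since the randomization date"; the period can be shortened or extended according to need. Section 9 (Removal of Participants) adds: "The interventionist and study PI will have weekly meetings/supervision to evaluate study progress". Those meetings also cover concerns about participant risk.

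**Contact in controls.** Section 5: "There will be no research staff-initiated contact with control subjects between baseline and follow up questionnaires". Section 9 (Randomization Procedures) agrees: "Research staff will not contact the families in the control condition again until the time of follow-up assessments at 3, 6, and 12 months". If a control family contacts staff with a safety concern, the same safety protocol applies as in the intervention arm.

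**How an AE comes to be recorded.** Under Safety Assessment in section 9, the process starts when staff learn of a concern. Under Removal of Participants, a parent's report that the child's ADHD symptoms "or their own parental mental health symptoms are worsening will be assessed clinically", after which the PI decides whether an AE is to be filed. Neither the text nor the Schedule of Events in the Appendix shows AE questions put to both arms.

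**Definition and review.** Section 10.1 defines an AE as an event that is "plausibly related to the research intervention and/or research procedures". The same paragraph says such events are documented regardless of judged relatedness. Section 10.2 gives the DSMB interim AE data to review and asks it to consider "any concerns for poor clinical outcomes among patients in a particular randomization condition".

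**The concern.** AE detection in this plan is passive: an event is recorded if someone happens to tell staff. The number of AEs found then depends on how often staff and family talk, and that differs between arms by design. A control family that completes its questionnaires by survey link could pass through the whole follow-up with little or no conversation with staff after learning its assignment.

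The definition adds a second, smaller source of imbalance. If plausible relatedness is needed before an event counts as an AE, staff may be slower to log an event in a family that received no intervention. The statement that relatedness does not matter for documentation points the other way, so two staff members could apply the paragraph differently.

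Three uses of the counts are exposed. Section 4.1 lists AEs among the things the pilot field-tests. The DSMB can recommend modifying or ending the trial. Section 10.3 requires a statement to the IRB on the overall pattern of AEs. An excess in PRE-CARE could be read as harm when it reflects closer observation, real harm could be dismissed as closer observation, and control events could be missed. The full trial could inherit the same collection method.

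**Working it through.** The documents give no AE rate, detection rate or safety power, so there is no stated figure to reproduce. The check counts contacts and then illustrates what the difference could do.

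**Step 1: scheduled contacts after baseline.** Three months is about 13 weeks; 13 / 2 = 6.5, so about 6 bi-weekly meetings (sections 5 and 8). Assessments fall at months 3, 6 and 12 in both arms (section 9).

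- Months 0 to 3: PRE-CARE 6 + 1 = 7; control 1.
- Months 0 to 12: PRE-CARE 6 + 3 = 9; control 3.

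The exit interview and as-needed contacts, which would raise the PRE-CARE count, are left out. So is early ending of meetings, which would lower it.

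**Step 2: detection model.** Assumptions: true risk is equal in both arms; each event occurs at a uniformly random time; each later contact reveals it with probability d, equal for all contacts and both arms; PRE-CARE meetings fall at weeks 2, 4, 6, 8, 10 and 12; assessments fall at weeks 13, 26 and 52. An event with k contacts still to come is found with probability 1 − (1 − d)^k.

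**Step 3: d = 0.2, events in months 0 to 3, counted at month 3.**

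- PRE-CARE: events in the six two-week intervals have k = 7, 6, 5, 4, 3, 2 contacts left; those in the final week have 1. Weighted sum: 2 × (0.790 + 0.738 + 0.672 + 0.590 + 0.488 + 0.360) + 1 × 0.200 = 7.48; divided by 13 = 0.575.
- Control: one contact left, 0.200.
- Ratio: 0.575 / 0.200 = 2.9.

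**Step 4: d = 0.2, events spread over 12 months, counted at month 12.**

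- Events in weeks 0 to 13 contribute 9.47 in PRE-CARE (k = 9 down to 3) and 13 × 0.488 = 6.34 in control.
- Weeks 13 to 26 contribute 13 × 0.36 = 4.68, and weeks 26 to 52 contribute 26 × 0.20 = 5.20, in each arm.
- PRE-CARE: (9.47 + 4.68 + 5.20) / 52 = 0.372. Control: (6.34 + 4.68 + 5.20) / 52 = 0.312. Ratio 1.19.

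**Step 5: range of d.**

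| d (assumed) | Month 3: PRE-CARE vs control | Ratio | Month 12: PRE-CARE vs control | Ratio |
|---|---|---|---|---|
| 0.2 | 58% vs 20% | 2.9 | 37% vs 31% | 1.19 |
| 0.4 | 82% vs 40% | 2.1 | 59% vs 56% | 1.07 |
| 0.6 | 93% vs 60% | 1.6 | 76% vs 74% | 1.02 |
| 0.8 | 98% vs 80% | 1.2 | 89% vs 89% | 1.00 |
| 1.0 | 100% vs 100% | 1.0 | 100% vs 100% | 1.00 |

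**Step 6: counts.** With 30 per arm and an assumed true risk of 10% in the first three months, 3 true events are expected per arm. Recorded by month 3: 3 × 0.575 = 1.7 against 3 × 0.20 = 0.6 at d = 0.2, and 3 × 0.82 = 2.5 against 3 × 0.40 = 1.2 at d = 0.4. The artefact is about one event.

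**Step 7: after the change.** If the comparison uses a common inquiry at months 3, 6 and 12, each arm has the same 3 contacts and the expected ratio is 1.0 for any d, provided d is equal across arms.

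**The case against.** The plan is less one-sided than it may first appear, and four stronger readings do not survive.

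- *Control events surface only at questionnaires.* Controls may call staff and then fall under the same safety protocol, and a treating provider may raise a concern in either arm. Medical record encounters and diagnoses are collected in both arms, though as utilization data and not as an AE source. The extra routes exist but are passive.
- *The definition excludes control events.* It covers research procedures, which controls also undergo. Its examples can occur in either arm, and documentation does not depend on judged relatedness. Section 10.2 adds suspected maltreatment without restriction by arm. What stands is an internal inconsistency that could be applied unevenly.
- *The DSMB will see biased AE tables by arm.* Section 10.2 states by-arm review for poor clinical outcomes and mentions no arm when it lists AE data. The main symptom scales are parent-reported on a schedule shared by both arms, so that review can rest on symmetric data. A by-arm reading of AE counts is plausible, but it is an inference.
- *The excess is large over the whole year.* Putting 9 and 3 contacts straight into 1 − (1 − d)^k gives ratios of 2.3, 1.8 and 1.5 for d = 0.1, 0.2 and 0.3. That requires every event to precede the first contact. With events spread over 12 months the ratios are 1.30, 1.19 and 1.12, because bi-weekly meetings that by default end at month 3 cannot reveal later events.

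It is also fair to say that this is a 60-family pilot with no planned group comparison and an independent DSMB with biostatistical expertise, and that contacts in both arms are already logged. This limits the consequence to a misreading of small counts. It does not supply the missing common inquiry.

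**Conclusion.** The concern holds as a structural weakness in AE collection. Followed exactly, the plan gives PRE-CARE about seven scheduled occasions for an event to emerge in the first three months and controls one, with no AE questions common to both arms and nothing to allow for the difference. More recorded AEs in PRE-CARE at equal true risk is the likely direction, not a demonstrated result.

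The size rests wholly on an assumed per-contact detection probability. The distortion is concentrated in the intervention period and is slight over 12 months unless detection per contact is low. It matters most at interim looks: the DSMB meets every six months, so its reviews can include families still in or just past the intervention period. No test or estimate in the statistical plan is affected. The change is worth making because it is cheap and because the pilot is meant to settle procedures for a larger trial.

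**What to change.** 1. Add the same short set of AE questions, covering the event types named in section 10.1, to the existing 3-, 6- and 12-month assessments in both arms. Ask about the whole interval since the previous assessment, including events already reported to staff.
2. Record the source of each event: common inquiry, intervention contact, participant-initiated contact, or provider.
3. Make relatedness a separate field and reconcile the two statements in section 10.1, so that the same entry rule applies in both arms.
4. Continue to report all AEs to the DSMB. For any between-arm comparison, use the commonly collected events as the primary basis, and list events found through intervention contacts separately beside the contact counts already logged under section 9. Using the common source exclusively would set aside events found in real time, so it should be the primary basis and not a filter.

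The cost is a slightly longer questionnaire and two additional data fields. Safety-related answers given remotely must be routed through the existing safety procedure, which takes some staff time. The common inquiry will also miss families who do not respond (section 12.2 allows for 25% attrition), so response numbers by arm should accompany the table.
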